2.3.8.2 Adverse Events of Special Interest

Adverse events of special interest (AESI) include gastrointestinal events, treatment failure due to dose reduction of study drug as defined in the protocol.

2.3.8.3 Other Safety Endpoints

- Vital signs, height, and weight:
 - Blood pressure, pulse, respiratory rate, height, weight, body temperature, and the presence of clinically significant abnormal values determined by an Investigator. Clinically significant abnormalities identified after the start of treatment will be reported as AEs.
- 12-Lead electrocardiogram (ECG):
 - An Investigator assessment of normal vs abnormal will be available as well as clinically significant vs not clinically significant. Abnormal, clinically significant ECG readings seen after the start of treatment will be recorded as AEs.
- Laboratory samples will include:
 - Hematology, serum chemistry, lipids, coagulation, and other. Clinically significant changes in laboratory values will be recorded by the clinical sites as AEs.
- Post-Treatment Withdrawal Flares:
 - The difference between Week 12 and Week 16 laboratory values for ALP, ALT, AST, and GGT will be summarized.

2.4 Study Day and Visit Windows

Summary tables will report data based upon the protocol scheduled time points (Baseline, Weeks 2, 4, 6, 8, 12, 16). Assessment will be assigned to these time points based upon the study day they are performed on. Study day is defined as

$$\text{Study Day} = \text{date of assessment} - \text{date of first treatment}.$$

The analysis windows used to report endpoints are outlined in Table 2. Assessments are assigned to an analysis window based upon the study day it occurred on as well as the treatment status at the time the assessment was performed. If more than one assessment is available within the range, the assessment closest to the target day is reported for the analysis window. If two observations exist with the same distance to the target day, the first observation is used.

Table 2 Analysis Windows

Visit	Study Day Range	Target Day	Treatment Status
Screening	< Day -1	First	Off Treatment ^a
Baseline Visit	Day 1	Day 1	Off Treatment ^a
Week 2	Day 2 to Day 21	Day 14	On Treatment ^b
Week 4	Day 22 to Day 35	Day 28	On Treatment ^b
Week 6	Day 36 to Day 49	Day 42	On Treatment ^b
Week 8	Day 50 to Day 70	Day 56	On Treatment ^b
Week 12	Day 71 to Day 90	Day 84	On Treatment ^b
Week 16	> Day 90	Day 112	Off Treatment ^c

^a Prior to first treatment.

^b After the start of treatment to 1 day after the last dose.

^c More than 1 day after the last dose.

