2.4.1 Definition of Baseline

Unless specified elsewhere, baseline is defined as the last available measurement prior to administration of study drug. For events that occur on the same day as the first administration of study drug (i.e. assessments performed at the Baseline visit), and for which the time of the assessment is not available, the assessment will be classified as pre-treatment, hence baseline. The exception to this rule will be AEs for which the event will be classified as a TEAE.

It should be noted that for the purpose of clinical management, the description of baseline varies in the protocol (e.g. inclusion/exclusion and Drug-Induced Liver Injury Monitoring). For analysis purposes, only the definition above will be used.

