3.4.1.1 Post-Treatment Withdrawal Flares

The difference between Week 12 and Week 16 laboratory values for ALP, ALT, AST, and GGT will be summarized using descriptive statistics.

3.4.2 *Pruritus VAS*

Change in Pruritus VAS will be summarized using descriptive statistics for the result and change from baseline. The proportion of subjects with improvement will be presented for subjects $>0.5\text{cm}$ at baseline. The proportion of subjects with worsening will be presented for subjects $\leq 0.5\text{cm}$ at baseline.

3.4.3 *Clinical Laboratory Evaluations*

Clinical laboratory results, including bile acids, will be summarized by type of laboratory assessment (hematology, serum chemistry, lipids, coagulation, other) and timepoint. Both central and local laboratory results will be used for the safety lab summaries. Summary statistics for actual values and changes from baseline will be tabulated by analysis window. Out of range clinical laboratory values based upon the normal range will be tabulated for each timepoint. These tables will utilize the normal ranges provided for the individual sample.

The proportion of subjects that cross the liver monitoring thresholds will be summarized. A listing of ALT values for subjects that meet the liver monitoring threshold will be presented similarly to the clinical laboratory listing. Baseline values will be summarized using last available measurement prior to administration of study drug.

3.4.4 *Vital Signs*

The observed data at baseline and change from baseline for each measurement day will be summarized with descriptive statistics.

3.4.5 *Electrocardiogram Results*

The overall ECG assessment (abnormal or normal) will be summarized by analysis window. The QT values will be summarized by analysis window as both the QT value and change from baseline.

3.4.6 *Pregnancy*

A listing of positive pregnancy tests results will be produced.

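### SAP Table 2: the Baseline row cannot be met, and off-treatment results up to Day 90 have no row, so an early stopper's 28-day follow-up can drop out of the by-window laboratory tables

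*SAP*

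**What the plan says.** SAP 2.4 computes study day as assessment date minus date of first treatment, with nothing added. It then sets two conditions for placing a result: "Assessments are assigned to an analysis window based upon the study day it occurred on as well as the treatment status at the time". The rows of Table 2 are:

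| Row | Study day | Status required |
|---|---|---|
| Screening | before Day -1 | before first treatment |
| Baseline | Day 1 | before first treatment |
| Weeks 2, 4, 6, 8, 12 | Days 2 to 90 in consecutive ranges | on treatment |
| Week 16 | after Day 90 | off treatment |

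On treatment means "After the start of treatment to 1 day after the last dose". For the Week 16 row, off treatment means "More than 1 day after the last dose".

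The timepoints that SAP 2.4 lists for summary tables are Baseline and Weeks 2, 4, 6, 8, 12 and 16, without Early Termination (ET). SAP 3.4.3 applies the windows to laboratory data: "Summary statistics for actual values and changes from baseline will be tabulated by analysis window", and "Out of range clinical laboratory values based upon the normal range will be tabulated for each timepoint". SAP 3.4.5 does the same for ECG: "The overall ECG assessment (abnormal or normal) will be summarized by analysis window". SAP 3.4, however, refers laboratory results to the timepoints of SAP Table 1, which has an ET column.

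SAP 2.4.1 defines the baseline value independently of Table 2, as the last measurement before study drug. For an untimed assessment on the first-dose day, "the assessment will be classified as pre-treatment, hence baseline".

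Protocol 7.2, 8.9 and footnote h of the Schedule of Events ask a subject who stops early to return 28 days after the last dose. Protocol 6.1.3 says that a subject who stops for gastrointestinal (GI) symptoms stays on the visit schedule.

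**The concern.** The Baseline row pairs a study day that falls after first dose with a status that ends at first dose. No assessment can satisfy both.

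The second gap has consequences for reporting. The protocol schedules blood draws after an early stop, and many fall on or before Day 90. Such a result is off treatment, so Weeks 2 to 12 reject it; it is too early for Week 16. It then appears in no by-window laboratory summary and no per-timepoint out-of-range count. The SAP justifies an on-treatment restriction for the primary ALP estimand (2.5.1.1) but gives no such reason for safety. The results lost belong to subjects who stopped early, often for intolerance. A programmer following the SAP must either drop them or devise a rule after the data are in.

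**Working it through.** **Inputs.** The study-day formula, row ranges and status footnotes come from SAP 2.4. Chemistry panels are at Days 14, 28, 42, 56, 84 and 112, and on-study ECGs are at Week 12 and ET only (Protocol Table 1). Follow-up is 28 days after last dose; I assume that the ±5 days given for Week 16 also applies to its equivalent after an early stop. L is the study day of the last dose.

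**1. Baseline row.** Study day on the first-dose date = date − same date = 0. Every pre-dose result therefore has study day ≤ 0, and none can be Day 1 and pre-dose. Days 0 and 1 match no row. Day -1 also matches none if the Screening row truly reads as strictly before Day -1; protocol screening runs through Day -1. If the formula added 1 from first dose onward, the first-dose date would become Day 1 and the Baseline row would work. Day -1 would still be unplaced.

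**2. Off-treatment gap.** On-treatment status ends at L + 1, and Week 16 starts at Day 91. Days L + 2 to 90 have no row: 90 − (L + 2) + 1 = 89 − L days. For L = 35 this is Days 37 to 90, or 54 days.

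**3. The 28-day follow-up (firm case).** Permitted days are L + 23 to L + 33, 11 days in all. Those at or before Day 90 have no row:

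| L | Permitted days | Days with no row |
|---|---|---|
| 57 | 80 to 90 | 11 of 11 |
| 62 | 85 to 95 | 6 of 11 |
| 67 | 90 to 100 | 1 of 11 |
| 68 | 91 to 101 | 0 of 11 |

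For L below 57 all 11 days are also lost. At exactly 28 days, the visit is lost when L + 28 ≤ 90, that is L ≤ 62.

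**4. Continued visits after a GI stop (conditional on Protocol 6.1.3).** With L = 35, the panels at Days 42, 56 and 84 have no row; Day 112 keeps Week 16. With L = 56, only Day 84 is lost. The Day 84 ECG has no row when L + 1 < 84, that is L ≤ 82.

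**5. The ET visit.** Held when drug is stopped, as Protocol 7.2 asks, it falls within L + 1 and is placed in an on-treatment row. The 28-day return includes no ECG (Protocol 8.8). On this route no scheduled ECG is lost.

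**6. Subjects affected (assumption).** Protocol 4.3 quotes GI discontinuation of 12% at this dose in NASH and none in PSC. Applied to 30 subjects: 0 × 30 = 0 to 0.12 × 30 = 3.6. These are other diseases, the NASH treatment lasted 18 weeks, and the documents do not give the timing of stops.

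**The case against.** The Baseline error changes no number. A reader might infer that baseline values or change from baseline are broken; SAP 2.4.1 shows that they are not. The Day -1 gap rests on one character in a text with damaged formulas, so it is stated conditionally.

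A reader might also infer that most of an early stopper's panels, and ECGs generally, are lost. The documents do not support that without qualification. It depends on Protocol 6.1.3, whereas 7.2 and 8.9 direct a subject who stops drug to an ET visit that includes study discharge, followed by one return visit. These passages conflict for a GI stop and must be reconciled. On the ET route only the 28-day return is at risk.

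It can be argued that the treatment-status rule is explicit and not limited to efficacy, so the exclusion is intended. The rule is explicit, but no safety exclusion is stated, and the SAP elsewhere shows interest in post-treatment data through its flare summary and its listing of off-treatment adverse events. The flare summary is not itself defective: it is defined as Week 12 against Week 16. It cannot fill the gap, because a Week 12 value needs L + 1 ≥ 71, and so does not exist for L ≤ 69.

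The ET column in SAP Table 1 might seem to rescue the data. It conflicts with SAP 2.4, and would not place the 28-day return, which 2.4 assigns by study day and not by visit name.

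The strongest point stands: clinically significant changes become adverse events, and the listings and the liver-threshold proportion can still capture these results.

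**Conclusion.** Wrong as written; minor. The Baseline row contradicts the SAP's own formula and needs a table correction only. The off-treatment gap makes the by-window laboratory and out-of-range tables incomplete for early stoppers. The firm loss is the 28-day follow-up: certain for a last dose by Day 57, possible through Day 67, absent from Day 68, given the ±5-day assumption. Losses of further panels and of a Day 84 ECG apply only if GI stoppers continue scheduled visits.

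The number of subjects is unknown; 0 to about 4 of 30 is a borrowed range for GI stops, and not all of those need fall early enough to matter. A reader might suspect an effect on the primary ALP result. There is none to correct: excluding off-treatment values there is the stated estimand.

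**What to change.** 1. **Day labels.** Either set Screening to Day -1 or earlier, Baseline to Day 0 pre-dose, and start Week 2 at Day 1, which matches the protocol's Day 0; or add 1 to the formula from first dose onward and make all of Table 2 consistent with it, including a place for Day -1.
2. **Post-treatment row, safety tables only.** Add a separate ET/post-treatment row for results more than 1 day after last dose and up to Day 90, not pooled into Weeks 2 to 12. Summarize one pre-stated value per subject, for example the one closest to last dose + 28 days. That alone recovers only some panels: with L = 35 the target is Day 63, so Day 56 is used and Days 42 and 84 are not. In the out-of-range table, therefore, count any subject with an out-of-range value at any time in that period.
3. **ET reporting.** Reconcile SAP 2.4 and 3.4.3 with SAP 3.4 and SAP Table 1 on whether ET is a reported timepoint.
4. **Protocol.** Reconcile 6.1.3 with 7.2 and 8.9 on visits after a GI stop, so that it is clear which results to expect.
5. **Leave the on-treatment ALP estimand unchanged.**

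Items 1 to 3 cost SAP wording and programming only; item 4 is a protocol clarification. The downside is that the new row may hold only a few subjects at differing times since last dose (2 to 55 days for L = 35), so it should be read as counts alongside the listings.

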**Table 7: Liver Monitoring Procedure – For Subjects with Normal or Near Normal Baseline ALT ( $\leq 60$  U/L)**

Event	Observation	Action
ALT becomes elevated	Isolated increase in ALT to $\geq 3$ x ULN (i.e., $\geq 180$ /L) with no increase in serum bilirubin and presence of symptoms of anorexia, nausea, fatigue, right upper abdominal discomfort or vomiting preceding or following the isolated increase in ALT to $\geq 3$ x ULN.	

Promptly repeat serum chemistry panel (ALT, AST, ALP, total bilirubin and direct bilirubin) within 2 to 5 days*

If subject lives remotely from the site, local labs may be obtained

The PI must review the local lab results promptly and local lab results must be entered into an unscheduled visit within the EDC

Continue investigational study drug

ALT remains elevated	If ALT remains $\geq 3$ x ULN	

Obtain serum chemistry panel (as above) and repeat 2 – 3 x/week until stable

Frequency of testing can be decreased to once per week or less if abnormalities stabilize or the subject is asymptomatic

Obtain detailed history of symptoms and prior or concurrent medical history

Obtain history of concomitant drug use including non-prescription medications, herbal & dietary preparations, alcohol use, recreational drug use, and special diets

Where appropriate, rule out acute viral hepatitis types A, B, C, D, & E, autoimmune or alcoholic hepatitis, NASH, hypoxic/ischemic hepatopathy & biliary tract disease

Obtain a history of exposure to environmental chemical agents

Obtain additional tests to evaluate liver function, as appropriate (e.g., INR, CBC with differential)

Continue investigational study drug

ALT decreases	ALT return to $< 3$ x ULN or baseline level	

Resume study-required laboratory assessments as per the Summary of Events table and continue investigational study drug

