2.3 Study Endpoints

The study endpoints are listed below, with greater detail concerning these endpoints provided in Sections 2.3.1 to 2.3.8.

Primary Efficacy Endpoint

The primary efficacy endpoint is the percent change in ALP at Week 12 compared to Baseline.

ALP Secondary Efficacy Endpoints

The ALP secondary efficacy endpoints are as follows:

- Absolute change in serum ALP at Week 12 compared to Baseline
- Proportion of subjects who have $\geq 20\%$ decrease in ALP from Baseline to Week 12
- Proportion of subjects who have $\geq 40\%$ decrease in ALP from Baseline to Week 12
- Proportion of subjects who normalize ALP at Week 12

Secondary Endpoints

- Change in total bilirubin from Baseline to Week 12
- Change in serum GGT between Baseline and Week 12
- Change in alanine aminotransferase (ALT) from Baseline to Week 12
- Change in aspartate aminotransferase (AST) from Baseline to Week 12
- Change in total cholesterol, low-density lipoprotein (LDL) cholesterol, and triglyceride levels between Baseline and Week 12
- Change in fibrinogen, c-reactive protein (CRP), haptoglobin, enhanced liver fibrosis (ELF) score, and serum immunoglobulins between Baseline and Week 12

Safety endpoints include the following:

- Changes from Baseline to Week 6 and Week 12 in GLOBE Score

HighTide Biopharma Pty. Ltd.
Protocol HTD1801.PCT013

- Changes from Baseline to Week 6 and Week 12 in pruritus (average and worst) as measured by pruritus visual analog score (VAS)
- Changes from baseline in vital signs, and clinical laboratory values
- Incidence of treatment-emergent adverse events (TEAEs) and serious adverse events (SAEs)
- PK parameters including $T_{1/2}$, C_{max} , and AUC
 - The analysis of these PK endpoints will be performed outside of this analysis plan.

Additional Analyses

- Proportion of subjects who have $\geq 10\%$ decrease in ALP from Baseline to Week 12
- Proportion of subjects at Week 12 who had Baseline ALP $\geq 1.67 \times$ ULN and have ALP $< 1.67 \times$ ULN, $\geq 15\%$ decrease in ALP and total bilirubin \leq ULN at Week 12.
- A plot of percent change in ALP at each timepoint through Week 12 for the ratio of current to prior dose of UDCA
- Proportion of subjects that crossed the liver monitoring thresholds will be summarized. The liver monitoring threshold is defined as ALT:
 - 3x ULN if the Baseline ALT is ≤ 60 U/L, or
 - 3x Baseline ALT if Baseline ALT is > 60 U/L

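### The by-window laboratory tables show one value per window and no worst post-baseline summary is planned, so they can miss on-treatment liver-test peaks

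*SAP*

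**What the plan says.** SAP 2.4 assigns each assessment to a window by study day and treatment status. Within a window, "If more than one assessment is available within the range, the assessment closest to the target day is reported for the analysis window", and for ties, "If two observations exist with the same distance to the target day, the first observation is used". The rule governs summary tables in general. It is not confined to efficacy or to scheduled samples. For Weeks 2 to 12 the sample must be on treatment, defined as "After the start of treatment to 1 day after the last dose". Week 16 takes samples after Day 90 that fall more than 1 day after the last dose.

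SAP 3.4.3 carries this into the safety laboratories: "Summary statistics for actual values and changes from baseline will be tabulated by analysis window", and "Out of range clinical laboratory values based upon the normal range will be tabulated for each timepoint". Neither section plans a maximum or worst post-baseline laboratory summary. The one subject-level liver summary, in SAP 2.3 and again in 3.4.3, is "Proportion of subjects that crossed the liver monitoring thresholds will be summarized". It is defined on ALT alone and is accompanied by an ALT listing for the subjects concerned.

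Protocol Table 7 says of a raised ALT: "Promptly repeat serum chemistry panel (ALT, AST, ALP, total bilirubin and direct bilirubin) within 2 to 5 days". If ALT stays up, the panel is repeated 2 to 3 times a week until stable. Table 8 has the same schedule for subjects with elevated baseline ALT. Local repeats are entered as unscheduled visits.

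**The concern.** Choosing the sample nearest the target day is sensible for a mean by visit, because it holds timing constant. It is a poor basis for describing liver safety, where the main question is how high a subject went. The extra samples under Protocol Section 10 are drawn because something looked abnormal, and they compete with the scheduled sample for a single place in the table.

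In a single-arm study of up to 30 subjects with liver disease, one missed excursion can change the safety picture, and there is no control arm to set it against. The SAP already reports TEAEs by worst grade per subject. The laboratory tables have no counterpart.

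**Working it through.** The plan gives no figure on this point. Its one design figure, power of at least 90%, reproduces at 94.1% (one-sample t-test, n = 30, 15/25 = 0.6 SD, one-sided 5%) and plays no part here.

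**Inputs.** Windows and target days from SAP Table 2: Week 2, Days 2–21 (target 14); Week 4, 22–35 (28); Week 6, 36–49 (42); Week 8, 50–70 (56); Week 12, 71–90 (84). Visit tolerance of ±3 days from the protocol schedule. First repeat 2 to 5 days later, from Protocol Tables 7 and 8.

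**1. One scheduled sample and one repeat.** Let the scheduled sample be *o* days from target (−3 to +3) and the repeat *r* days later (2 to 5). That gives 7 × 4 = 28 pairings per window and 5 × 28 = 140 in all.

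- The repeat is reported only if |o + r| < |o|. This holds for o = −3 with all four values of r, and for o = −2 with r = 2 or 3. That is 6 per window, and 5 × 6 = 30.
- The repeat leaves the visit's window once each for Weeks 2, 4 and 6 (o = +3, r = 5, landing on Days 22, 36 and 50), never for Week 8, and three times for Week 12 (Days 86 + 5, 87 + 4 and 87 + 5). That is 6.
- In the remaining 140 − 30 − 6 = 104 the scheduled value is reported and the repeat is not.

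The shares are 104/140 = 74%, 30/140 = 21% and 6/140 = 4%. In 134 of 140 pairings one of the two values is missing from that visit's row. With repeats 2 to 3 times a week, still only one value per window is shown.

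**2. Direction.** The reported value is one of the observed values, so it cannot exceed the maximum in the window. It equals the maximum only when the peak is also the sample nearest the target. By-window maxima and counts above the upper limit are therefore correct or too low.

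**3. Examples (hypothetical values).**

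- ALT 185 U/L on Day 28, 260 on Day 31 and 320 on Day 34. The Week 4 value is 185, or 185/53 = 3.5 times the central laboratory ULN of 53. The peak was 320/53 = 6.0 times. The Week 4 out-of-range count is still right; the height is not.
- ALT 320 on Day 25 and 200 on the Day 28 repeat. The Week 4 value is 200. Here the repeat is kept and the scheduled peak is lost.
- Total bilirubin within range on Day 28 and above 1.21 mg/dL on Day 31. Week 4 counts the subject as in range.

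**4. After a permanent stop.** With last dose on Day L, samples from Day L + 2 are off treatment. Weeks 2 to 12 exclude them, and Week 16 does not open until after Day 90. With L = 42, Days 44 to 90 (90 − 44 + 1 = 47 days) belong to no window. The follow-up visit 28 days after the last dose also falls in the gap whenever L + 28 ≤ 90, that is L ≤ 62. Tables 7 and 8 require monitoring to continue after a stop until abnormalities resolve, so these are samples the protocol asks for.

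**The case against.** The strongest reply is that nothing is lost. SAP 2.4 only chooses which value a table shows. SAP 3.4.3 refers to a clinical laboratory listing and adds the ALT threshold listing. Clinically significant laboratory changes become adverse events (SAP 2.3.8.3), and TEAEs are shown by worst CTCAE grade. Protocol 12.4.4 promises continuous summaries and selected in-or-out-of-range categories, and the SAP delivers both. With up to 30 subjects, each excursion can be reviewed individually.

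Much of this stands, and it rules out several stronger readings that a reader might infer:

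- *The mandated repeats are discarded.* They are not. They remain in the database and listings, and in 30 of 140 pairings the repeat is the value reported.
- *The ALT threshold proportion misses subjects.* The documents do not say so. It is a subject-level proportion and, unlike its neighbours in SAP 3.4.3, is not described as by window or timepoint. The SAP is silent on which samples feed it: an ambiguity, not a documented loss. On the Table 7 pathway the triggering ALT is already at least 180 U/L, so if that sample is the one reported, the crossing is visible even in windowed data.
- *Most of two weeks of repeats vanish from every window.* Only Week 8 has 14 days after its target (70 − 56). Weeks 2, 4 and 6 have 7 and Week 12 has 6. Later samples pass into the next window.
- *Local results or their own ranges are ignored.* SAP 3.4.3 already uses central and local results and each sample's own normal range.

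The backstops are nevertheless partial. The threshold summary and its listing cover ALT only, although bilirubin, INR and ALP also enter the stopping rows of Tables 7 and 8. Adverse event capture depends on the investigator's judgement of clinical significance, and SAP 2.3.8.2 names no hepatic event of special interest. The protocol's DILI monitoring eCRF has no planned summary in the SAP. Listings let a reader find a peak but do not summarise it.

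**Conclusion.** The point holds for the by-window and by-timepoint laboratory tables. They can miss an on-treatment peak, they cannot overstate one, and no other planned laboratory summary supplies it. The gap is widest for AST, ALP, total bilirubin and INR, and for samples after an early permanent stop.

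The 74% and 21% describe calendar pairings, not an expected share of subjects. They assume that all offsets are equally likely, that the repeat interval runs from the scheduled sample, and that the subject stays on treatment. Understatement in the actual data is possible, not certain: it needs a subject with repeat samples whose peak is not the one nearest the target day. The documents give no basis for predicting how many such subjects there will be. The primary endpoint analysis, power and alpha are not at issue.

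**What to change.** In SAP 2.3 and 3.4.3:

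1. Add a worst post-baseline summary and an any-post-baseline out-of-range count for ALT, AST, ALP, total bilirubin and INR. Derive both from all post-baseline samples, scheduled and unscheduled, including those taken after treatment stops. Mark whether each worst value fell on or off treatment, so that the on-treatment peak stays identifiable.
2. State that the ALT threshold-crossing proportion uses all post-baseline samples.
3. Keep the closest-to-target rule for means and changes by visit.

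The cost is SAP wording and one extra derived record per analyte. Maxima tend to be somewhat higher in subjects sampled more often, and a table footnote should say so. No new data are needed, and power, alpha and clinical management are unchanged.
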